4.1.4 Treatment start/stop dates

If there are no treatment dates available in the administration page of the CRF, date of randomisation will be imputed as the start of treatment date, if it is known that the subject received study drug (information recorded in the administration page of the CRF or any information from monitoring).

If the end of treatment date is missing in the administration page of the CRF, it will be imputed with the start date + administration duration of the same administration record.

If the end of treatment date is missing in the treatment termination page of the CRF, the latest stop date from administration page (including imputed ones) would be imputed.

4.1.5 Tables and listings presentation

The treatment groups will be displayed as in table 1.

Listings will display all data contained in the CRF, excluding collected information on the screen failure subjects and subjects randomised and not treated. Screen failure and not treated subjects will be displayed in a separate listing. Listings will be ordered by treatment, centre, subject ID, and visit date or event/medication start date.

4.1.6 Analysis Sets

The analysis of the primary endpoint will be performed for the Per Protocol set (PPS) and tested at a one sided alpha level of 2.5% with a 15% non-inferiority margin. A sensitivity analysis will be performed on the Full Analysis Set (FAS). All secondary endpoints will be analysed on the FAS and the PPS. All statistical tests will be performed at a 5% level (2-sided).

All safety analyses will be performed on the Safety Set.

4.1.7 Analysis of Subgroups

4.1.8 Methods for Handling and imputation of Missing Data

Incomplete or missing data will not be imputed unless otherwise specified (Treatment start date (see 4.1.4.), medical history and concomitant medications (see 4.4), adverse events (see 4.7.1)).

4.2 Subject Disposition, Randomisation Assignment and Subject Populations

Subject disposition data will be collected on the study termination CRF page when a subject complete or discontinue from the study. The subject disposition data will be summarised. The following data will also be presented in the listings:

- Date of randomisation, randomisation number, planned treatment group, actual treatment received, and first administration date and time in the randomisation listing.
- Data of subjects included and excluded in FAS, PPS, and Safety Set with the reason of exclusion of any analysis set in the analysis population listing.

4.3 Demographics and Baseline Subject Characteristics

Subject demographic and baseline characteristics data (sex, race, age, weight, and height) will be collected on the demographics CRF. The following baseline laboratory parameters Hb, TSAT, Serum ferritin, hsCRP will be collected on the laboratory CRF.

The demographics will be summarised and listed (demographic listing includes dates of informed consent).

Body mass index (BMI) will be calculated from weight and height as below

$$\text{BMI} = \text{weight(kg)} / [\text{height(m)}]^2$$

4.4 Medical History and Concurrent Medical Conditions

All medical history (stopped prior to study drug administration) and concurrent medical conditions (started before dosing and ongoing or started after dosing) will be coded using the MedDRA (version 19.1).

Medical history identified as cause of IDA will be summarised separately by system organ class and preferred term.

All medical history and concurrent medical conditions (including the ones identified as cause of IDA) will be summarised by system organ class and preferred term. Also all medical history and concurrent medical conditions will be listed separately (Medical history identified as cause of IDA will be flagged). Prior and Concomitant Procedures will be listed separately.

Missing dates/partial dates will be handled per below.

Imputation of Start Dates:

- If only the month and year are specified, 1st of the month will be used.

- If only the year is specified, January 01 will be used.
- If the start date is completely unknown, no imputation will be performed.

Imputation of Stop Dates:

- If only the month and year are specified, then use the last day of the month.
- If only the year is specified, then use December 31 of that year.
- If the stop date is completely unknown, no imputation will be performed.

4.5 Study Drug Exposure and Compliance

All individual dosing information will be listed and will include planned dose, dose form, Planned /Actual kit No., the start/end date and time of study drug administration, duration of administration, arm used for injection/infusion and actual volume administered. Any reasons for incomplete dose will be listed if applicable. A subject is defined as treatment compliant if he or she has taken at least 80% and not more than 120% of the investigational product dosage planned for that interval. The dose of study drug information (cumulative planned dose, cumulative actual dose, days on treatment, duration of study participation, Total no. of injections/infusions received, treatment compliance rate, and compliance rate category (<80%, 80 to <120 %, >=120 %)) will also be summarised by treatment group.

Cumulative treatment compliance percentage will be calculated as:

$$\text{Cumulative treatment compliance} = 100 \times \frac{\text{Total Iron administered (mg)}}{\text{Total Iron planned (mg)} (1)}$$

(1) For subjects who withdraw the study the Total planned Iron is the Iron they should receive up to their discontinuation day.

For subjects in FCM arm with a body weight <50kg and who withdrew on Day 8 or Day 15, they may have withdrawn the study before or after drug administration and therefore, will be considered compliant in either case unless consideration is required for under or over dosing (if they received the dose planned that day, the dose of the day should be added to the Total planned Dose, If they did not received it, the dose of the day should not be added to the Total planned dose.)

For subjects in the IS arm, drug administrations could happen on any day within each week windows. The following table shows the total doses a subject could have received by day of withdrawal. If a subject has a Total Iron received equal to any possible total dose or equal to the calculated Total planned Iron (by Ganzoni formula) if he/she withdrew after day 28, he should be considered as compliant. Otherwise, if the total received dose is different to all possible doses at the time of withdrawal, the possible dose which is the closest to the received dose should be considered as the total planned dose.

Day of study withdrawal	Possible Total doses*			
1	200			
2	200	400		
3 to 6	200	400	600	
7	400	600		
8	600	800		
9	600	800	1000	
10 to 12	600	800	1000	1200
13	800	1000	1200	
14	1000	1200		
15	1200	1400		

16	1200	1400	1600	
17 to 19	1200	1400	1600	1800
20	1400	1600	1800	
21	1600	1800		
22	1800	2000		
23	1800	2000	2200	
24 to 26	1800	2000	2200	2400
27	2000	2200	2400	
28	2200	2400		

*: If the minimal possible dose is greater than the planned dose calculated by Ganzoni formula, the planned dose by Ganzoni formula should be consider as the total planned dose.

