9.2.2 Treatment Procedures

Subjects randomised to receive FCM will receive the first administration of FCM at baseline (Day 1), and the second and third dose at Day 8 and Day 15, if needed according to the dosing matrix (see Table 2, Section 7.2.1, Arm A: Ferric Carboxymaltose).

Subjects randomised to IS will have their iron deficit calculated according to the Ganzoni formula (see Section 7.2.2, Arm B: Iron Sucrose). The doses will be split into injections of 200 mg iron and administered three times a week until the calculated dose has been given to the subject. The cumulative Venofer dose is to be rounded up or down to the nearest 200 mg. During these dosing visits, no additional data will be collected or procedures performed, except for ongoing information on AEs or change in concomitant medications, including dose. Note: Application of IS and FCM at any visit should be done after all assessments as per Schedule of Event, Table 1, especially blood draw for laboratory assessments, have been performed.

For both treatment groups, time of start and end of administration (including any interruptions) and volume administered (i.e. incomplete dose including reason) must be recorded.

During post-baseline visits at 2, 4 and 6 weeks (± 3 days), the following assessments will be performed:

- Vital signs
- Laboratory assessments (haematology, chemistry, iron parameters, urinalysis)
- AEs and concomitant medications
- ECG (only Week 4)

See

Table 1: Schedule of Events for full details of protocol required procedures and applicable visits (and timings).

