3.3 Per Protocol Set

The Per-Protocol Set (PPS) is defined as all subjects in the FAS with a study drug compliance between 80 and 120% and do not have any major protocol violations ([appendix 1](#)).

The subjects in the PPS will be analysed based on the treatment that they were randomised to.

As per protocol, blood samples had to be drawn before study drug administration (when planned). All laboratory efficacy assessments (Hb, Ferritin, and TSAT) that are measured from a blood sample

taken after the study drug administration will not be considered for any efficacy analysis for both PPS and FAS. The subjects will still be in the PPS if they do not have a major protocol deviation.

For subjects who took prohibited concomitant medication, all laboratory efficacy assessments (Hb, Ferritin, and TSAT) will be censored after the prohibited medication start date for both PPS and FAS. The subjects will still be in the PPS if they do not have a major protocol deviation.

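### The same-day withdrawal allowance in the compliance rule omits heavier FCM subjects who also have a Day 8 dose, so some could fail the per-protocol gate where comparable IS subjects pass

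*SAP*

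**What the plan says.** SAP 3.3 defines the PPS as "all subjects in the FAS with a study drug compliance between 80 and 120% and do not have any major protocol violations". SAP 4.1.6 makes the PPS the set for the primary non-inferiority test (one-sided 2.5%, 15% margin) and the FAS the sensitivity set.

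SAP 4.5 calls a subject compliant with "at least 80% and not more than 120% of the investigational product dosage planned for that interval". Compliance is 100 × iron administered / iron planned. A footnote gives the denominator for early leavers: "For subjects who withdraw the study the Total planned Iron is the Iron they should receive up to their discontinuation day". It does not say whether the discontinuation day itself is included.

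Two arm-specific rules follow.

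- **FCM.** The rule begins "For subjects in FCM arm with a body weight <50kg and who withdrew on Day 8 or Day 15". Its reason is that such a subject may have left before or after that day's administration. A dose given that day enters planned iron; a dose not given does not.
- **IS.** A table lists the possible totals by withdrawal day, and a subject whose received iron matches any listed total is compliant. For Day 8 the totals are 600 and 800 mg. If nothing matches, "the possible dose which is the closest to the received dose should be considered as the total planned dose".

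Protocol 9.2.2 says FCM subjects receive "the second and third dose at Day 8 and Day 15, if needed according to the dosing matrix". That matrix is Table 2 in Protocol 7.2.1, and its Day 8 doses are not confined to subjects under 50 kg.

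**The concern.** The reason for the FCM allowance, that withdrawal can fall either side of dosing on the same day, has nothing to do with body weight. It applies equally to a 65 kg or 80 kg subject with a Day 8 dose. As written, the heavier subjects get no allowance, while the IS table gives the equivalent allowance at every weight.

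Because compliance gates the primary analysis set, the gap could remove some early FCM leavers and keep their IS counterparts. Someone who leaves on Day 8 is unlikely to have gained 2 g/dL (a judgement; no Day 8 response rate is given). Removing such subjects from FCM only would raise the FCM responder rate and move the difference towards non-inferiority.

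**Working it through.** **1. The plan's sample size, for denominators.** With 70% in both arms, margin 0.15, one-sided 2.5% and 80% power: n = (1.960 + 0.842)² × 2 × 0.70 × 0.30 / 0.15² = 146.5, so 147 per group. Then 147 / 0.80 = 183.75, so 184. Both match SAP 2.4.

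**2. FCM subjects who leave on Day 8 before dosing.** Doses are from Protocol Table 2 and its footnote. Received iron is the Day 1 dose.

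| FCM cell | Day 1 (mg) | Day 8 (mg) | Day 8 counted | Day 8 not counted | Allowance written? |
|---|---|---|---|---|---|
| 35 to <50 kg, either Hb group | 500 | 500 | 500/1,000 = 50% | 500/500 = 100% | Yes |
| 50 to <70 kg, Hb <10 | 1,000 | 500 | 1,000/1,500 = 66.7% | 100% | No |
| 50 to <70 kg, Hb ≥10 | 1,000 | none | 1,000/1,000 = 100% | 100% | Not needed |
| ≥70 kg, Hb <10 | 1,000 | 1,000 | 1,000/2,000 = 50% | 100% | No |
| ≥70 kg, Hb ≥10 | 1,000 | 500 | 1,000/1,500 = 66.7% | 100% | No |

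Three cells fall below 80% when Day 8 is counted. A Day 15 dose exists only below 50 kg with Hb <10, so the written rule already covers Day 15. The gap is confined to Day 8.

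**3. Does the discontinuation day count?** The SAP does not say. If it did not count, every cell would be 100% and the exception for subjects under 50 kg would be unnecessary. The exception therefore implies that the day counts.

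**4. IS subjects who leave on Day 8.** With 600 mg: 600/600 = 100%. With 800 mg: 800/800 = 100%. With 400 mg: 400/600 = 66.7%, a fail. So the IS rule excuses the dose of the day, but not doses missed in the first week.

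**5. Can these subjects reach the PPS?** Protocol 5.4.2 asks early leavers to have all End of Study assessments, which include haematology. A Day 8 Hb falls in the SAP's Week 2 window (Day 2 to Day 21) and would meet the post-baseline requirement of the FAS. Without that sample the subject is outside both sets. Appendix 1 also lists visits not done as a major deviation, without saying whether this covers visits after withdrawal.

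**6. Size per subject.** At 70%, 103 of 147 respond (0.70 × 147 = 102.9). Dropping one FCM non-responder gives 103/146 − 103/147 = 70.55% − 70.07% = 0.48 points. Three give 103/144 − 103/147 = 71.53% − 70.07% = 1.46 points.

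**7. A result near the margin.** Assume 147 other subjects per arm, with 95 FCM and 103 IS responders, plus k early non-responders kept in IS only. The difference is 95/147 − 103/(147 + k). The lower bound uses the SAP's interval (Newcombe, continuity-corrected).

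| k | Difference | Lower bound |
|---|---|---|
| 0 | −5.4% | −16.4% |
| 2 | −4.5% | −15.5% |
| 5 | −3.1% | −14.2% |

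If the five were kept in both arms, the bound would be −16.2%. So k = 5 would matter, but only for a result already close to −15%. The documents give no value for k.

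**The case against.** **The IS table is not lenient.** A reader might infer that it passes under-dosed subjects, since 200 mg on Day 6 or 600 mg on Day 12 counts as full compliance when 600 or 1,200 mg was possible. The documents do not support this. The protocol asks for three IS doses a week without fixing weekdays, and SAP 4.5 says doses may fall on any day within each week. On Day 6, Days 6 and 7 remain for two doses; on Day 12, Days 12 to 14 remain for three. These subjects have missed no required dose. Using the most front-loaded schedule as denominator, or imposing a fixed calendar, would label adherent IS subjects non-compliant.

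**Not every heavier FCM subject is affected.** Those of 50 to <70 kg with Hb ≥10 have no Day 8 dose and stay at 100%.

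**Exclusion is an inference.** It rests on counting the discontinuation day. That is the more natural reading, but it is not stated.

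**The bias is conditional.** Early leavers need a post-baseline value. If visits not done after withdrawal count as major deviations, early leavers drop out of the PPS in both arms whatever their compliance. The same test is also run on the FAS, which has no compliance gate and gives a check on any distortion.

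**The 120% boundary does not gate anything.** The summary uses "compliance rate category (<80%, 80 to <120 %, >=120" %, which puts exactly 120% (for example 1,200 of 1,000 mg) in the top class although the definition accepts it. A reader might take this as a further exclusion. It is a descriptive label; PPS entry depends on "study drug compliance between 80 and 120" %.

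All of this stands as a limit on the point. None of it explains why the FCM allowance should depend on body weight.

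**Conclusion.** The same-day allowance is incomplete. It covers FCM subjects under 50 kg but not three heavier dosing cells with a Day 8 dose, while IS subjects have the equivalent allowance at any weight. On the reading that the exception implies, the omitted subjects score 66.7% or 50% and fail the gate to the primary analysis set.

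The likely effect is small. It touches only FCM subjects in those cells who leave on Day 8 before dosing, at about 0.5 points each against a 15-point margin. One to three such subjects (an assumption) would give about 0.5 to 1.5 points. This assumes that the discontinuation day counts, that these subjects have a post-baseline value, that no other rule removes them, and that they are counted as non-responders. Where it operates, the direction favours non-inferiority. The documents do not support a claim that the primary result is materially biased or that the IS rule is at fault.

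**What to change.** In SAP 4.5, before database lock:

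1. Delete the body-weight condition from the FCM rule. For every FCM subject who withdraws on a day with a scheduled dose, that dose then enters planned iron only if it was given. Keep the existing caveat on under- and over-dosing. The three affected cells move to 100%.
2. State whether the discontinuation day counts in planned iron.
3. Leave the IS table unchanged.
4. As a minor alignment, set the descriptive categories to below 80%, 80 to 120% inclusive, and above 120%.

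The cost is one deleted phrase, one added sentence and a relabelled table. Dosing, data collection and sample size (147 evaluable, 184 randomised per group) do not change. A few early FCM leavers, probably non-responders, may stay in the PPS, which is slightly less favourable to FCM.

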4.6 Efficacy Analysis

4.6.1 Primary Efficacy Analysis

The primary endpoint is the percentage of subjects achieving an increase in Hb of $\geq 2\text{g/dL}$ (responders) from baseline at any time up to Week 8. The non-inferiority test will be applied to the difference (FCM - IS) between the proportions of subjects meeting the primary endpoint using the PPS and FAS. Non-inferiority will be determined if the lower bound of the 95% CI of this difference is above the non-inferiority margin as defined -15%. The difference in proportions between the FCM and Venofer groups from baseline at any time up to Week 8 and its one-sided 97.5% confidence intervals (CIs) will be computed using the Wilson score method with continuity correction described by Newcombe (1998).

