2.1 Design

An efficacy study in Caucasian subjects by Evstatiev et al, 2011 [15] demonstrated that FCM administered using a simplified dosing formula (as proposed in this study) was superior to IS dosed using the Ganzoni formula (at multiple 200 mg iron doses). However, since no data are available on the use of FCM in Chinese patients, a non-inferiority design has been chosen for this study, assuming that FCM treatment is at least as good as IS in Chinese subjects. A randomised design was chosen to reduce bias in baseline differences between the treatment groups.

Due to the differences in posology between the study drug (FCM) and the comparator (IS) additional administrations may be required for subjects receiving IS. In a 65 kg subject with Hb of 9 g/dL at screening, FCM would require 2 individual doses of FCM (1,000 mg iron followed by a single dose of 500 mg iron 1 week later). However, if the same subject was randomised to receive IS, the cumulative dose required (as per label) would be 1,436 mg iron which would require 7 individual 200 mg iron doses (i.e., bi-weekly dosing) starting on Day 1.

Therefore, this study will utilise an open-label design to avoid unnecessary IV placebo injections. This reduces the burden of requiring additional subject visits to both groups (as subjects receiving IS will need more dosing visits than subjects in the FCM group) as well as removing the potential for infection and other side-effects that may result from an IV placebo injection.

IV iron products are designed to deliver, in a controlled way, iron to the body and to replenish iron stores and as a consequence increase Hb concentration. Therefore, the study primary endpoint is the percentage of subjects achieving an increase in Hb \geq 2g/dL (responders) from baseline at any time up to Week 8. Since knowledge of the study drug will not impact this objective parameter, in addition to the fact that all subjects will be receiving IV iron, the open-label design is considered to be the most appropriate design for this study.

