2.4 Sample Size Determination

To assess the non-inferiority of FCM compared to IS in the proportion of subjects who will have an increase from baseline in Hb of $\geq 2\text{g/dL}$ at any time up to Week 8 (responders), the following assumptions have been made:

- Subjects that will be included in the study will be mainly subjects with Gastro Intestinal (GI) disorders and women with heavy uterine bleeding (HUB). The responder rate after IS treatment is expected to be 70%. This is based on the mean of the proportion of responders in the 2 studies described below in IDA subjects with inflammatory bowel disease (IBD) and IDA subjects with HUB respectively.

In study FER-IBD-07-COR, which compared FCM to IS in IDA subjects with IBD, the proportion of subjects who had an increase from baseline in Hb $\geq 2\text{g/dL}$ at Week 8 was 72% in FCM group and 55% in IS group (Per Protocol Set (PPS)). Seventy three percent in the FCM group and 58% in the IS group had an increase of at least $\geq 2\text{g/dL}$ at any time up to Week 8.

In study 1VIT04002/1VIT04003, which compared FCM to oral iron in IDA subjects with HUB, 82% of subjects in the FCM group had an increase from baseline in Hb $\geq 2\text{g/dL}$ at any time up to Week 6. Although no subjects in this study were treated with Venofer, and no other data are available from studies in which HUB subjects are treated with Venofer, it has been assumed that Venofer would have the same response rate as FCM in this subject population.

- The non-inferiority margin for the difference in the proportion of responders between FCM and IS was set to -15%. This margin will ensure a treatment effect for FCM ($70 - 15 = 55$) greater than 33%, the upper bound of the 95% confidence interval (CI) of the proportion of responder of an estimated placebo effect, by more than half the effect itself ($33 + 16.5 = 49.5$). The placebo effect was estimated as follows:

In study 1VIT07017 which compared FCM to Standard Medical Care (SMC) in IDA subjects with HUB or post-partum, there were 55 subjects in the SMC group who did not receive any Iron treatment. Of these, 50 had an Hb assessment at Day 30. At Day 30 the proportion of non-treated subjects with an Hb increase ≥ 2 g/dL was 22% (11/50) with a 95% CI from 11% to 33%.

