The sample size is based on showing non-inferiority in the difference in the proportion of subjects achieving an increase in Hb of ≥ 2 g/dL at any time up to Week 8 between FCM and IS. Applying a test at a one-sided alpha level of 2.5%, and a -15% non-inferiority margin, 147 subjects per group will have 80% power to detect that FCM is non-inferior to IS with an expected IS responder proportion of 70%. The total sample size is 368 (184 per treatment group), taking into account an estimated drop-out rate of 20% of the randomised subjects.

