2.5 Randomisation and Blinding

This study is an open-label, randomised controlled study to assess the impact of FCM in correcting IDA compared with Venofer.

Subjects will be allocated one of the following treatments: FCM or IS. The randomisation allocation ratio will be 1:1 and the randomisation will be blocked by centre. They will be assigned to site via Interactive Response Technology system during study. Totally, there will be 600 blocks with 4 as block size (15 block per centre). The randomisation schedule was generated and maintained by Tigermed according to Tigermed SOPs.

Table 1 presents the treatment group labels and Table 2 presents the visit labels that will be used in all output.

Table 1: Study Treatments

Studied Treatment	Treatment Label
FCM	FCM
Venofer	IS

Table 2: Study Visits

Visit Number (title)	Visit Label
Visit 1 (Screening)	Screening
Visit 2 (Day 1)	Baseline
Visit 3 (Week 2)	Week 2
Visit 4 (Week 4)	Week 4
Visit 5 (Week 6)	Week 6
Visit 6 (Follow-Up, Week 8)	End of study

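### The primary responder difference is analysed without baseline Hb, which gives up available precision; separately, its continuity correction was not in the sample size, so power is about 79% rather than 80%

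*SAP*

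**What the plan says.** SAP 4.6.1 takes the difference in the proportion of subjects with an Hb rise of at least 2 g/dL at any time up to Week 8. Its confidence interval is "computed using the Wilson score method with continuity correction", following Newcombe, and non-inferiority is concluded if the lower limit lies above -15%. No covariate or stratification factor is named. The per-protocol set is primary and the full analysis set is the sensitivity analysis (SAP 4.1.6).

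The sample-size text in SAP 2.4, repeated in Protocol 11.2, says "147 subjects per group will have 80% power to detect that FCM is non-inferior to IS with an expected IS responder proportion of 70"%. It names no formula and mentions no continuity correction.

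SAP 4.6.2 does use covariates for secondary endpoints. Change in Hb is modelled with baseline Hb and site, and iron-deficiency correction, a binary outcome, is modelled by logistic regression with baseline ferritin, baseline TSAT and site. Protocol 11.7.1 leaves the details of the primary analysis to the SAP, so the two documents do not conflict.

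**The concern.** A responder is defined by a change from baseline Hb, so a subject's starting value plausibly predicts whether a 2 g/dL rise is reached. The SAP accepts this for the continuous Hb endpoint and accepts a logistic model for another binary endpoint, but uses neither for the primary comparison. Randomisation is blocked by centre only (SAP 2.5), so the design does not balance baseline Hb. If it is prognostic, an unadjusted comparison has a wider interval than the same data could give, and the primary conclusion depends on the width of that interval.

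The second point is one of consistency. The sample size rests on one test and the SAP plans another, slightly more conservative one, so the stated power is not quite the power of the planned analysis.

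**Working it through.** **Inputs**
- Test level: "Applying a test at a one-sided alpha level of 2.5"% (SAP 2.4).
- Margin: "The non-inferiority margin for the difference in the proportion of responders between FCM and IS was set to -15"% (SAP 2.4).
- Stated size: "147 subjects per group will have 80% power" (SAP 2.4).
- Control rate: "The responder rate after IS treatment is expected to be 70"% (SAP 2.4).
- FCM rate: no number is given. Protocol 2.1 speaks of "assuming that FCM treatment is at least as good as IS in Chinese subjects". Taking 70%, a true difference of zero, reproduces the stated size.
- Allocation: "The randomisation allocation ratio will be 1:1" (SAP 2.5). Drop-out is 20% (SAP 2.4).

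**1. Reproducing the stated size.** With the uncorrected normal formula,

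n = (1.96 + 0.8416)² × 2 × 0.7 × 0.3 / 0.15² = 146.5, rounded up to 147.

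147 / 0.8 = 183.75, rounded up to 184 per arm, 368 in total. This matches. The continuity-corrected version is (n/4) × [1 + √(1 + 4/(0.15n))]² with n = 146.5, which gives 159.6, so 160 per arm and 200 randomised per arm. That does not match, so the stated size contains no correction.

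**2. What the correction does to the interval.** Newcombe's lower limit is d − √[(p₁ − l₁)² + (u₂ − p₂)²], where l₁ and u₂ are Wilson limits for the FCM and IS proportions. At 103/147 responders in both arms (0.7007):
- Without correction the Wilson limits are 0.6223 and 0.7688, and the lower limit is 10.4 points below the estimate.
- With correction they are 0.6188 and 0.7719, and the distance is 10.9 points.

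**3. Exact power and type I error.** These come from full enumeration of two binomial arms of 147, counting a success when the lower limit exceeds -15%.

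| Method | Power at 70%/70% | Type I error at 55% v 70% |
|---|---|---|
| Newcombe, corrected (planned) | 78.7% | 2.22% |
| Newcombe, uncorrected | 81.0% | 2.70% |
| Wald | 80.2% | 2.37% |
| Miettinen-Nurminen | 80.3% | 2.50% |
| Farrington-Manning | 80.6% | 2.56% |

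The planned interval has 79.8% power at 152 per arm and 80.2% at 153. The shortfall at 147 is 80 − 78.7 = 1.3 points, or 153 − 147 = 6 evaluable subjects per arm.

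**4. Adjusting for baseline Hb.** The documents give no prognostic strength, so the slopes here are assumptions. Let standardised baseline Hb be normal, with the logit of response linear in it (slope b per SD, either sign) and a mean response of 70%. Let R² be the variance of the predicted probability divided by 0.7 × 0.3. Approximate power without a continuity correction is Φ(0.15 / √[0.42(1 − R²)/147] − 1.96).

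| Assumed slope b | R² | Approximate power |
|---|---|---|
| 0 | 0% | 80.1% |
| 0.3 | 1.8% | 80.9% |
| 0.6 | 6.7% | 82.8% |
| 0.9 | 13.4% | 85.4% |
| 1.2 | 20.5% | 88.2% |

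Simulating the standardised logistic estimate itself at 147 per arm gave about 80% power with no prognostic effect and about 82-89% for slopes of 0.3 to 1.2. Type I error was 2.2-2.9% (Monte Carlo SE about 0.25 points). A larger run of 20,000 trials per setting gave 80.5% power at slope 0, 81.4% to 88.3% at slopes 0.3 to 1.2, and type I error of 2.4-2.6% (SE about 0.11 points). I therefore read the range for slopes of 0.3 to 1.2 as about 81-89%.

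**The case against.** The best defence is that the planned method is published, fully specified and conservative. It holds type I error at 2.2%, whereas the uncorrected Newcombe interval reaches 2.7%, and in an open-label non-inferiority trial that is a legitimate choice. This stands: dropping the correction is a trade-off.

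The power shortfall is also small beside other uncertainties. With the planned interval at 147 per arm, power is 73.1% if the common rate is 58% and 90.2% if it is 82%. If FCM responds at 71% or 72% against 70%, power is 84.1% or 88.5%. At 160 evaluable per arm it is 82.0%. This stands too.

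The gain from adjustment rests on assumed slopes and could be near zero. That is correct; the claim is only that the cost is low and the likely direction favourable.

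The proposed model also leaves out site, although randomisation is blocked by centre and the secondary models include it. SAP 2.5 lists 600 blocks at 15 per centre, which is 40 centres; 368 / 40 is about 9 subjects each. Site terms in a logistic model would be sparse, so leaving them out of the primary model is reasonable.

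A reader might infer four stronger things that the documents do not support:
- That ignoring baseline Hb causes the 78.7%. It does not: the sample size was unadjusted as well.
- That baseline Hb sets the dose in both arms. Dose is set from screening Hb (synopsis; Protocol 7.2.1 for FCM). The baseline sample is separate, and its results are not back in time for eligibility (Schedule of Events, footnote 1).
- That chance imbalance in baseline Hb biases the result. Under randomisation it is sampling error, which the unadjusted interval already covers.
- That 147 is a miscalculation or that more subjects must be randomised. The figure reproduces from its stated inputs.

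**Conclusion.** Both points hold, and they should be kept apart.

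The main one is lost precision. The primary analysis omits a covariate that is available for everyone, is built into the response definition and is already used in the same SAP. Adjusting would take power at 147 per arm from about 80% to about 81-89% if the log-odds slope per SD of baseline Hb is between 0.3 and 1.2. If baseline Hb is not prognostic, power stays at about 80%. The slope range is an assumption.

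The minor point is exact: at 70%/70% and 147 per arm, the planned interval has 78.7% power. That assumes equal true rates and exactly 147 evaluable subjects per arm. The 1.3-point gap is a matter of accurate reporting and does not make the trial inadequate.

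**What to change.** In SAP 4.6.1, pre-specify as primary the marginal (standardised) risk difference, FCM minus IS, from a logistic model with treatment and baseline Hb as defined in SAP 4.1.2. Give its 95% CI, either by the delta method with a variance valid for the marginal effect or by bootstrap, and compare the lower limit with -15%. Apply it to the PPS and the FAS, keep the unadjusted interval as supportive, and add the matching tables to Appendix 3. Because the trial is open-label, the change should be dated before database lock and before outcomes are reviewed by arm.

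The cost is modest programming and a type I error near the nominal 2.5% instead of the conservative 2.2%. A short simulation at the margin should confirm this before sign-off. The estimated quantity, margin and sample size do not change.

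If the corrected interval stays primary, restate power as about 79% in SAP 2.4, Protocol 11.2 and the synopsis, and consider the adjusted estimate as supportive.
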